7.2.3. Measures to Minimize Bias

This is non-randomized open-label study. The analysis of tumor response and progression-free survival will be based on tumor response assessments performed by the investigator according to standardized, objective response criteria (RECIST 1.1). In addition, in the event of a positive study outcome, an additional assessment of tumor response and progression may be performed by an independent review committee (IRC) blinded to investigator assessments.

7.2.4. Withdrawals and Replacement of Patients

Every effort should be made within the bounds of safety and patient choice to have each patient complete the study. An explanation will be recorded for each patient taken off study treatment or discontinuing the study.

Patients who discontinue study prior to the first disease assessment for reasons unrelated to study treatment (i.e., adverse events deemed unrelated to study treatment, withdrawal of consent, lost to follow-up, withdrawal due to administrative reasons, etc.) will be excluded from the response-evaluable population and may be replaced. Patients who discontinue study prior to the first disease assessment due to treatment-related adverse events, symptomatic deterioration (adverse events due to progression), or death will be included in the response evaluable population.

7.2.4.1. Discontinuation of Study Treatment

Reasons for discontinuation of study treatment include:

- Progressive disease, as assessed by the treating investigator in accordance with RECIST 1.1 criteria ([Appendix 3](#)); in Cohorts 2-5 an exception may be granted as described in [Section 7.2.4.1.1](#).
- Symptomatic deterioration (clinical progression):
 - Note: This category is applicable to patients with a global deterioration of health status requiring discontinuation of treatment. However, per RECIST 1.1 ([Appendix 3](#)), symptomatic deterioration is not a descriptor of an objective response; it is a reason for stopping study therapy. Thus, every effort should be made to continue disease

assessments per protocol until documented objective progression or initiation of alternate therapy.

- Receipt of alternate anti-cancer treatments
- Withdrawal request by the patient or the patient's legal representative
 - Note: Withdrawal of consent for continued treatment should be differentiated from withdrawal of consent for study follow-up, and every effort should be made within the bounds of safety and patient choice to have each patient complete the study follow-up.
- Adverse Event
- Physician Decision
- Non-compliance of the patient
- Pregnancy
- Death, otherwise not explainable by the above options
- Patient lost to follow-up (see below)
- Treatment-limiting toxicity (Cohorts 2-5)

Patients who discontinue study treatment should be seen for an End of Treatment Visit. Patients who discontinue study treatment without progression of disease as per RECIST 1.1 should continue Disease Assessment Visits until criteria for disease progression are met or alternate therapies are initiated (see [Table 1](#), and [Table 2](#)).

7.2.4.1.1 Allowance for Permitting Continued Study Drug Treatment in Cases of Apparent Progressive Disease

As described in [Section 5.6.4](#), accumulating evidence indicates a minority of patients treated with immunotherapy may derive clinical benefit despite initial evidence of progression per RECIST ([Appendix 3](#)). Therefore, in order to ascertain whether true progression has occurred, or whether a treatment mediated inflammatory/immune mediated antitumor reaction (pseudoprogression) might have preceded a tumor response, patients with apparent progression who have no additional conventional treatment options may continue study treatment and complete the subsequent disease assessment on schedule, provided the following criteria are met:

- Investigator-assessed clinical benefit. The assessment of clinical benefit should take into account whether the patient is clinically deteriorating and unlikely to receive further benefit from continued treatment.
- Patient is tolerating study drug.
- All decisions to continue treatment beyond initial progression must be discussed with the Celldex Medical Monitor and the patient, and the patient must sign an informed consent form for continued treatment after initial progression. Patients can only continue study treatment beyond initial progression if they have no additional conventional treatment options.

- Patients should discontinue study therapy upon further evidence of further progression, defined as an additional 10% or greater increase in tumor burden volume from time of initial progression (including all target lesions and new measurable lesions). For this assessment, new lesions are considered measurable at the time of initial progression if the longest diameter is at least 10 mm (except for pathological lymph nodes, which must have a short axis of at least 15 mm). Any new lesions considered non-measurable at the time of initial progression may become measurable and therefore included in the tumor burden measurement if the longest diameter increases to at least 10 mm (except for pathological lymph nodes, which must have an increase in short axis to at least 15 mm).
- For statistical analyses that include the investigator-assessed progression date, patients who continue treatment beyond initial investigator-assessed, modified RECIST 1.1 defined progression will be considered to have investigator-assessed progressive disease at the time of the initial progression event.

7.2.4.2. Discontinuation from Study

Reasons for patient removal from the study include:

- Request of the patient or the patient's legal representative (withdrawal of consent for the study follow-up)
- Patient lost to follow-up
 - A subject should be considered lost to follow up only after multiple efforts have been made to contact the subject to assess his/her health status after failure of the subject to attend scheduled visits. If after two documented phone calls the investigative site is still unable to contact the subject, a certified letter should be sent to his/her home for immediate response. If there is still no response, the subject is to be considered lost to follow up. A record of the subject being lost to follow up should be noted in the source documents along with the phone contacts and the returned certified mail (if sent back).

7.2.5. Completion of Study

It is anticipated that the enrollment period will be approximately 54 months. All patients will be followed with regard to survival until death, discontinuation from study follow-up, or termination/completion of study. Patients who die or complete the study follow-up through study closure will be considered to have "completed" the study.

The study will be declared complete when sufficient data is obtained to conclude the study; this is estimated at approximately two years from the date when the last patient in the study discontinues study treatment. Premature termination of this study may occur because of a regulatory authority decision, drug safety issues, or at the discretion of Celldex. In addition, Celldex retains the right to discontinue development of glembatumumab vedotin or varlilumab at any time.

[REDACTED]

[REDACTED]

[REDACTED]

[REDACTED]

[REDACTED]

[REDACTED]

[REDACTED]

[REDACTED]

[REDACTED]

[REDACTED]

8.3. Nivolumab

8.3.1. Description, Packaging, and Labeling

Nivolumab will be obtained from commercial supply and handled/stored in a fashion consistent with packet insert and institutional policies. The following sections are based on package insert (dated July 2017). However, investigators are responsible for referencing the complete and most current package insert for full guidance regarding potential toxicity and dosing of nivolumab.

Nivolumab is available as 40 mg/4 mL and 100 mg/10 mL solution in a single-dose vial.

8.3.2. Storage and Handling

Nivolumab does not contain a preservative. Store nivolumab under refrigeration at 2°C to 8°C (36°F to 46°F). Protect from light by storing in original package until time of use. Do not freeze or shake.

After preparation, store the nivolumab infusion either:

- At room temperature for no more than 8 hours from the time of preparation. This includes room temperature storage of the infusion in the IV container and time for administration of the infusion or
- Under refrigeration at 2°C to 8°C (36°F to 46°F) for no more than 24 hours from the time of infusion preparation.

Do not freeze.

8.3.3. Preparation and Administration

Preparation of the Dilution

Visually inspect nivolumab solution for particular matter and discoloration prior to administration. Nivolumab is a clear to opalescent, colorless to pale-yellow solution. Discard the vial if the solution is cloudy, discolored, or contains extraneous particulate matter other than a few translucent-to-white, proteinaceous particles. Do not shake the vial.

- Withdraw the required volume of nivolumab and transfer into an intravenous container
- Dilute nivolumab with either 0.9% Sodium Chloride Injection, USP or 5% Dextrose Injection, USP to prepare an infusion with a final concentration ranging from 1 mg/mL to 10 mg/mL.
- Mix diluted solution by gentle inversion. Do not shake.
- Discard partially used vials or empty vials of nivolumab.

Administration

Administer the infusion over 60 minutes through an intravenous line containing a sterile, non-pyrogenic, low protein binding in-line filter (pore size of 0.2 micrometer to 1.2 micrometer). Do not co-administer other drugs through the same intravenous line. Flush the intravenous line at the end of infusion.

Glebatumumab vedotin and nivolumab will be administered as separate infusions when dosing occurs on the same day. Nivolumab should be the first infusion and glebatumumab vedotin administered at least 30 minutes later as the second infusion. Patients should be observed on Cycle 1 Day 1 for at least 2 hours after the last study drug, and for at least 1 hour at all subsequent dosing visits. For additional details on glebatumumab vedotin administration please see [Section 8.1.3](#).

8.4. Pembrolizumab

8.4.1. Description, Packaging, and Labeling

Pembrolizumab will be obtained from commercial supply and handled/stored in a fashion consistent with packet insert and institutional policies. The following sections are based on package insert (dated July 2017). However, investigators are responsible for referencing the complete and most current package insert for full guidance regarding potential toxicity and dosing of pembrolizumab.

Pembrolizumab is available as 50 mg lyophilized powder in single-use vial for reconstitution and as 100 mg/4 mL (25 mg/mL) solution in single-use vials.

8.4.2. Storage and Handling

Pembrolizumab does not contain a preservative. Store the reconstituted and diluted solution from the pembrolizumab 50 mg vial either:

- At room temperature for no more than 6 hours from the time of reconstitution. This includes room temperature storage of reconstituted vials, storage of the infusion solution in the IV bag, and the duration of infusion.
- Under refrigeration at 2°C to 8°C (36°F to 46°F) for no more than 24 hours from the time of reconstitution. If refrigeration, allow the diluted solution to come to room temperature prior to administration.

Store the diluted solution from the 100 mg/4 mL vial either:

- At room temperature for no more than 6 hours from the time of dilution. This includes room temperature storage of reconstituted vials, storage of the infusion solution in the IV bag, and the duration of infusion.
- Under refrigeration at 2°C to 8°C (36°F to 46°F) for no more than 24 hours from the time of reconstitution. If refrigeration, allow the diluted solution to come to room temperature prior to administration.

Do not freeze.

8.4.3. Preparation and Administration

Preparation of the Dilution

Reconstitution of pembrolizumab for injection (lyophilized powder):

- Add 2.3 mL of Sterile Water for Injection, USP by injecting the water along the walls of the vial and not directly on the lyophilized powder (resulting concentration 25 mg/mL).
- Slowly swirl the vial. Allow up to 5 minutes for the bubbles to clear. Do not shake the vial.

Preparation for intravenous infusion:

- Visually inspect the solution for particulate matter and discoloration prior to administration. The solution is clear to slightly opalescent, colorless to slightly yellow. Discard the vial if visible particles are observed.
- Dilute pembrolizumab injection (solution) or reconstituted lyophilized powder prior to intravenous administration.
- Withdraw the required volume from the vial(s) of pembrolizumab and transfer into an intravenous (IV) bag containing 0.9% Sodium Chloride Injection, USP or 5% Dextrose Injection, USP. Mix diluted solution by gentle inversion. The final concentration of the diluted solution should be between 1 mg/mL to 10 mg/mL.
- Discard any unused portion left in the vial.

Administration

Administer infusion solution intravenously over 30 minutes through an intravenous line containing a sterile, non-pyrogenic, low-protein binding 0.2 micron to 5 micron in-line or add-on filter. Do not co-administer other drugs through the same infusion line.

Glembatumumab vedotin and pembrolizumab will be administered as separate infusions when dosing occurs on the same day. Pembrolizumab should be the first infusion and glembatumumab vedotin administered at least 30 minutes later as the second infusion. Patients should be observed on Cycle 1 Day 1 for at least 2 hours after the last study drug, and for at least 1 hour at all subsequent dosing visits. For additional details on glembatumumab vedotin administration please see [Section 8.1.3](#).

[REDACTED]

[REDACTED]

[REDACTED]

[REDACTED]

[REDACTED]

[REDACTED]

[REDACTED] e

[REDACTED]

[REDACTED]

[REDACTED]

[REDACTED]

[REDACTED]

[REDACTED]

[REDACTED]

[REDACTED]

[REDACTED]

[REDACTED]

8.6. Dose Modifications

8.6.1. Glebatumumab vedotin

Glebatumumab vedotin dose reductions in individual patients for toxicity are permitted; intra-patient dose escalations are not. Any patient who requires a dose reduction will continue to receive a reduced dose for the remainder of the study. A maximum of two dose reductions are allowed. If a patient requires more than two dose reductions, they should be discontinued from treatment.

Dose reduction levels are as follows:

- Starting dose: 1.9 mg/kg
- First dose reduction: 1.3 mg/kg
- Second dose reduction: 1.0 mg/kg

Patients experiencing the following require dose reduction:

- Grade 3 or 4 non-hematological drug-related toxicity not resolving to Grade 2 or less within 72 hours of initiation of supportive care. Exceptions to this criterion include alopecia and other toxicities of non-vital organs after discussion with the medical monitor
- Grade 4 neutropenia lasting > 5 days or associated with fever > 100.5°F

- Grade 4 thrombocytopenia
- Patients that develop Grade 2 or 3 neuropathy will have dosing held until neuropathy improves to \leq Grade 1, and will be restarted with a dose reduction. Patients with Grade 4 neuropathy should have treatment discontinued altogether.
- Other events that, in the opinion of the treating investigator, warrant dose modification

8.6.3. PD-1 Targeted Checkpoint Inhibitor

The PD-1 targeted CPI should be administered in accordance with institutional standard practice with reference to the manufacturer's package insert. Dosing of these CPIs should not be omitted or significantly delayed to accommodate other study treatments being administered in this study. In Cohorts 3 and 5, no more than 3 doses of nivolumab or 2 doses of pembrolizumab should be missed prior to initiation of glembatumumab vedotin therapy.

8.6.4. CDX-301

There will be no CDX-301 dose modifications. If discontinued, CDX-301 will not be reinstated. CDX-301 should not be administered if marked leukocytosis, e.g., WBCs greater than 50,000 cells/mm³, is observed. Any \geq Grade 3 injection site reactions thought related to CDX-301 warrant discontinuation of CDX-301 treatment.

Doses missed for any reason should not be made up; the next CDX-301 dose should be administered as per the treatment plan.

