7. Assessment of gpNMB expression and/or dendritic cells will be performed by IHC, retrospectively, at a central laboratory on FFPE Pre-entry and On-treatment tumor samples. Additional analyses performed centrally may also include, but are not limited to, gpNMB expression by Reverse Transcriptase Polymerase Chain Reaction (RT-PCR), examination of tumor markers using IHC or other molecular analyses, evaluation of tumor infiltrating leukocyte populations, biomarkers related to immune activation and localization of glembatumumab vedotin, CR011, or MMAE at the tumor site in post-treatment samples. For these analyses, fresh Pre-entry and On-treatment samples will need to be cut into two pieces. Sample collection, processing and shipping instructions will be provided separately. Tumor tissue samples will be collected until such time Celldex informs the sites that further data is not needed.
8. Fresh pre-entry samples must be obtained within 12 weeks prior to study entry, be subsequent to the last systemic anticancer therapy received, and be post-tumor progression. On-treatment biopsies must be obtained on Cycle 1 Day 7 (+/- 1 day). On-treatment biopsies in Cohort 5 may be collected at a different time point depending on the results obtained in Cohort 4. If so, then any change will be communicated to the Investigators and sites. Sites of sample collection must be soft tissue tumor or visceral lesions that can be attained with acceptable clinical risk (as judged by the investigator). The site chosen should not have been previously irradiated and must be distinct from RECIST 1.1 target lesions.
9. At recurrence, biopsy and central analysis of recurrent tumor is optional but strongly encouraged. Similarly, in the event of tumor resection or biopsy performed per standard of care anytime during treatment or following tumor progression, submission of these tissue samples for central analysis is strongly encouraged.
10. Medical history includes demography, melanoma history, previous surgeries/therapy, and pre-existing diseases. At Cycle 1, Day -6, medical history is updated prior to administration of study drug.

11. Complete physical exam should be performed at screening; thereafter, symptom-directed exams are acceptable.
12. Assessments do not need to be repeated if completed within the previous 24 hours as part of the screening assessment.

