20. Imaging-based evaluation per RECIST 1.1 should be performed. Contrast-enhanced Computed Tomography (CT) of the chest, abdomen, and pelvis, as well as all other suspected disease sites is required. Magnetic Resonance Imaging (MRI) exams of the brain, abdomen, and pelvis can be performed in lieu of a CT; however, MRI exams of the chest are not recommended. In the event that a chest MRI is performed, a non-contrast chest CT is strongly recommended to evaluate the lung parenchyma. Brain and/or bone scans are required for any patients with a history of metastases to bone and/or brain or where symptomatology raises the suspicion for bone and/or brain metastases. Lesions identified on bone scans should be confirmed by a CT or MRI at baseline, and, if identified as target lesions due to soft tissue component, they should continue to be followed by the same methodology (i.e., CT or MRI scan). However, bone lesions followed as non-target disease may be subsequently followed by bone scans only. Lesions that cannot be imaged but are assessable by clinical exam may be assessed by color photography including a ruler (preferred method) or measured with calipers. Normally, all target and non-target disease sites should be evaluated at each assessment. However, for patients with non-target bone disease, bone scans need only be repeated every twelve to eighteen weeks, or more frequently if clinically indicated. The same method of assessment and the same technique should be used to characterize each identified and reported lesion at baseline and during follow-up. Target lesions selected for tumor measurements should be those where surgical resection or radiation are not indicated or anticipated.
21. Unless otherwise specified, all study assessments should be performed prior to administration of study treatment(s), and may be performed up to 24 hours prior to treatment administration if assessments remain within the specified visit window.
22. The intent is for CDX-301 to be administered for 5 consecutive days on Monday through Friday, followed by glembatumumab vedotin treatment (and PD-1 targeted CPI for Cohort 5) on the following Monday. CDX-301 administration is allowed on weekend days if the site has the ability to do so. Ideally, CDX-301 should be administered at approximately the same time each day. Patients should be observed on Day -6 prior to Cycle 1 for at least 1 hour after CDX-301 injection, and for at least 30 minutes at all subsequent CDX-301 doses.

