8.8. Potential Toxicity and Management of Toxicity

Potential toxicity and guidance for the management of toxicity is summarized below. However, the glembatumumab vedotin, varlilumab, and CDX-301 Investigator’s Brochures, and the PD-1 targeted CPI package insert, are the Single Reference Safety Documents that provides complete and relevant information about the known safety profile of each agent. Updates to these data will be provided as revisions to the Investigator’s Brochures and through Investigational New Drug (IND) Safety Reports submitted to the investigator by Celldex, rather than by amendment to this section of the protocol.

Glembatumumab vedotin-related toxicities observed in previous studies have included neutropenia, alopecia, rash, pruritus, diarrhea, nausea, vomiting, constipation, fatigue/asthenia, pyrexia, anorexia, neuropathy and dysgeusia. Serious hematologic, gastrointestinal and dermatologic toxicity have occurred in 3-4% of treated patients. Infrequent but serious events have included fatal cases of toxic epidermal necrolysis and renal failure; severe or fatal sepsis (some cases were associated with pneumonia or urinary tract infection); and infusion site extravasation.

Toxicity related to varlilumab has been generally low-grade, and has included fatigue, arthralgia, nausea, decreased appetite, diarrhea, headache, vomiting, pyrexia, rash, pruritus, cough and neuropathy. Asymptomatic laboratory changes including lymphopenia, changes in liver function tests, and increases in lipase and amylase have occurred. Additional events consistent with an immune-mediated mechanism, such as hyperthyroidism, hypothyroidism, colitis, and infusion reaction, have been infrequently reported.

CDX-301 was generally well-tolerated in all prior studies. In the Celldex-sponsored phase 1 study in 30 healthy volunteers, treatment-related toxicity was infrequent, and reported only at the 25 and 75 µg/kg/day dose levels. One Grade 3 event, community acquired pneumonia, was considered treatment-related. No additional infections, DLT, treatment-related SAE, or treatment-related Grade 3 toxicity were reported. All other treatment-related adverse events were Grade 1 and included lymphadenopathy, diarrhea, injection site erythema, folliculitis, and dry mouth.

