Investigators should be cognizant of the potential for unpredicted acute and chronic toxicity associated with the combination of glembatumumab vedotin and immunotherapy. Patients receiving glembatumumab vedotin and immunotherapy should be closely monitored for toxicity. Patients should be advised to immediately report symptoms such as unexplained abdominal pain, diarrhea, nausea or vomiting, severe rash, vision changes or signs of a potential infection, such as a fever of 100.5°F or greater, chills, cough, or pain on urination. Patients with unexplained symptoms such as fatigue, myalgias, impotence, mental status changes, or constipation should be investigated for the presence of thyroid, pituitary or adrenal endocrinopathies. Visual complaints should be investigated by an ophthalmologist. Laboratory tests must be performed as outline in Schedule of Assessments and results reviewed prior to dosing. Patients in Cohort 1 should be monitored for at least 1 hour following the last administration of study drug to monitor for infusion reaction/cytokine release syndrome/hypersensitivity reaction. Patients in Cohorts 2-5 should be observed on Cycle 1 Day 1 for at least 2 hours after the last study drug, and for at least 1 hour at all subsequent dosing visits. In Cohorts 4 and 5, patients should also be observed for at least 2 hours after the first dose of CDX-301, the first dose of glembatumumab vedotin, and for at least 1 hour at all other dosing visits. Infusions should be given in a monitored setting that has ready access to an intensive care unit in case of a severe infusion reaction.

Toxicity should be aggressively worked-up and appropriately managed per the guidelines provided in the Glembatumumab Vedotin Investigator's Brochure, the Varlilumab Investigator's Brochure, the package insert for the PD-1 targeted checkpoint inhibitor, and the CDX-301 Investigator's Brochure to include the following:

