- Detailed guidance for management of immune-mediated adverse events (irAEs) are provided in the varlilumab Investigators Brochure.
- Detailed guidance for management of irAEs following nivolumab treatment are provided in the package insert. Management of such include administration of corticosteroids based on the severity of the reaction. In addition, nivolumab treatment should be withheld for: moderate immune-mediated pneumonitis, hepatitis, adrenal insufficiency, nephritis, or renal dysfunction; moderate or severe immune-mediated colitis, hypophysitis, or new-onset neurological signs or symptoms; severe immune-mediated hyperglycemia or rash. If any of these events increase in severity or become life-threatening, or if immune-mediated encephalitis or severe infusion reaction occurs, then nivolumab treatment should be permanently discontinued. Manage changes in thyroid function with initiation of thyroid hormone replacement as needed (nivolumab package insert, July 2017).
- Detailed guidance for management of irAEs following pembrolizumab treatment are provided in the package insert. Management of such include administration of corticosteroids based on the severity of the reaction. Changes in liver enzyme elevations due to immune-mediated hepatitis should be monitored, with treatment withheld or discontinued based on severity. In addition, pembrolizumab treatment should be withheld for: moderate immune-mediated pneumonitis, nephritis, or hypophysitis; moderate or severe colitis; severe hyperglycemia or hyperthyroidism. If any of these events increase in severity or become life-threatening, or if severe or life-threatening infusion reaction or skin reactions including Stevens-Johnson syndrome and toxic epidermal necrolysis occur, then nivolumab treatment should be permanently discontinued. Manage changes in thyroid function with initiation of thyroid hormone replacement as needed (pembrolizumab package insert, July 2017).

- Leukocytosis, especially monocytosis, is expected during administration of CDX-301 and may be particularly pronounced when combined with other hematopoietic growth factors. Hematological parameters, including WBC and differential, should be monitored in subjects receiving CDX-301. CDX-301 should not be administered if marked leukocytosis, e.g. WBCs greater than 50,000 cells/mm³, is observed.

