9. CONCOMITANT THERAPY

While on study, when clinically appropriate, patients should strictly follow the study-prescribed treatment regimen. Therefore, patients should not receive additional investigational agents or anti-cancer therapies, unless recurrence/progression of disease warrants discontinuation of study treatment and commencement of alternate therapies.

Subjects may continue to use any ongoing medications not prohibited by the inclusion/exclusion criteria. During study treatment, patients may receive supportive care to include bisphosphonates, hematologic and anti-infectious support and pain management. Anti-emetics and steroids, if needed, for chemotherapy premedication are also permitted.

Growth factor support is permitted and should be administered with consideration to the American Society of Clinical Oncology ([Robert, Thomas et al.](#)) guideline on the use of hematopoietic colony-stimulating factors ([Smith, Khatcheressian et al. 2006](#)). If growth factor support for neutropenia is required while the patient is also being treated with CDX-301 (Cohorts 4 and 5), then white blood cell counts and differentials should be closely followed.

Efforts should be made to maintain stable doses of concomitant medications during the course of treatment with glembatumumab vedotin, varlilumab, the PD-1 targeted checkpoint inhibitor, and CDX-301.

If surgical intervention or localized radiation become indicated (either for palliation or down-staging of previously non-resectable tumor), these interventions are permitted, but should be avoided if clinically feasible until after the 12 week response assessment. A tumor response assessment should be conducted prior to any intervention, in order to document progression and/or confirm an objective response. Patients who undergo surgical resection or radiation in the absence of progression may continue to receive study treatment until remaining lesions meet criteria for progression of disease.

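### Table 2 schedules hematology only before the first injection of each five-day CDX-301 course, so no scheduled count can trigger the leukocytosis rule within a course: a low-severity, cheap safety improvement

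*Protocol*

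**What the plan says.** The withholding rule is in Protocol Section 8.6.4: "CDX-301 should not be administered if marked leukocytosis" is observed, with more than 50,000 cells/mm3 as the example. Section 8.8 repeats it, says that leukocytosis is to be expected during administration, and warns that it may be more marked with other hematopoietic growth factors.

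On monitoring, Section 8.8 says "Hematological parameters, including WBC and differential, should be monitored in subjects receiving CDX-301", without naming days. For laboratory tests in general, the same section says "Laboratory tests must be performed as outline in Schedule of Assessments and results reviewed prior to dosing". Sections 9 and 9.4 add that if growth factor support is needed during CDX-301, "white blood cell counts and differentials should be closely followed"; again no days are named.

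CDX-301 is injected on Days -6 to -2 and Days 15 to 19. The Table 2 hematology row restricts sampling in those two columns to Day -6 and Day 15. The other scheduled counts are at screening, Cycle 1 Day 1, Cycle 1 Day 7, Day 1 of Cycle 2 and later cycles, and End of Treatment. Footnote 15 requires hematology results to be reviewed before dosing but adds no sample. Footnote 21 places assessments before study drug.

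**The concern.** A rule that depends on a laboratory value can act only when blood is drawn. A site that follows Table 2 will hold one count from before the first injection of a course, then give five injections, then draw again. If the count climbed during the course, the site would have no scheduled result on which to withhold the remaining injections. A site that reads Section 8.8 as asking for more must choose its own days, so monitoring would differ between sites.

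Course 2 deserves some thought. It follows the first glembatumumab vedotin dose, neutropenia is a known toxicity of that drug, and growth factor support is permitted. That is the setting in which Section 8.8 expects a larger rise, yet Table 2 has no count between Day 15 and Cycle 2 Day 1. Safety and tolerability are also the primary objective of Cohort 4. What is at stake is patient safety and consistent safety data; no efficacy estimate or error rate is affected.

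**Working it through.** The plan states no figure on this point, so the check is a count of dosing days against the Table 2 hematology row.

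1. **Injections.** Days -6 to -2 (5) plus Days 15 to 19 (5) = 10 per patient.
2. **Counts on injection days.** Day -6 and Day 15. Each is taken before the first injection of its course.
3. **Injections with no count taken after their course began, apart from the first of each course.** Course 1: Days -5, -4, -3, -2 = 4. Course 2: Days 16, 17, 18, 19 = 4. Total 8 of 10.
4. **The two courses differ.** Before course 2 there are counts on Days 1, 7 and 15, all after exposure to course 1, so a carry-over would be seen. A rise caused by course 2 itself would not be seen before its fifth injection.
5. **Gap to the next count.** Footnote 22 gives the weekly pattern: "The intent is for CDX-301 to be administered for 5 consecutive days on Monday through Friday, followed by glembatumumab vedotin treatment" on the following Monday. Day -6 to Day 1, Monday to Monday, is 7 days; Day 15 to Cycle 2 Day 1 (Day 22) is 22 - 15 = 7 days. With the +3/-1 day visit window the gap is 7 - 1 = 6 to 7 + 3 = 10 days. Footnote 12 says "Assessments do not need to be repeated if completed within the previous 24 hours as part of the screening assessment", and footnote 21 says that assessments "may be performed up to 24 hours prior to treatment administration if assessments remain within the specified visit window". At the widest reading, these allowances stretch the range to 6 - 1 = 5 and 10 + 1 = 11 days. The lower end stays at 6 if the sample itself must fall inside the visit window, as footnote 21 says.
6. **Visit windows do not close the gap.** Day 1 less one day still follows Day -2, Day 7 plus one day precedes Day 15, and Cycle 2 Day 1 less one day follows Day 19. Section 7.1 names Day 14, which is not a CDX-301 dosing day either.
7. **Effect of the remedies.**

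| Hematology days in the courses | Injections 2-5 with no in-course count | Longest run of injections between counts |
|---|---|---|
| -6, 15 (now) | 8 of 10 | 5 |
| plus -2, 19 | 6 of 10 (Days -5, -4, -3, 16, 17, 18) | 4 |
| plus -4, 17 as well | 2 of 10 (Days -5, 16) | 2 |

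8. **Scale.** Cohort 4: 8 x 10 to 12 = 80 to 96 of 100 to 120 injections. Cohort 5, only if it opens: 8 x 30 = 240 of 300.

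**The case against.** The strongest reply is that the rule is reactive. It bars CDX-301 when marked leukocytosis has been observed and does not demand a count before every injection. Counts on Days 1, 7 and 15 would identify a patient with a marked response to course 1 before course 2 starts. Section 8.8 already asks for white cell monitoring in subjects receiving CDX-301, directly beside the rule, and staff see every patient at each injection. In-course counts help only if 50,000 can be passed within about four days of starting a course, and nothing visible shows that it can. The summary of 30 healthy volunteers reports one Grade 3 pneumonia and otherwise says "All other treatment-related adverse events were Grade 1 and included lymphadenopathy, diarrhea, injection site erythema, folliculitis, and dry mouth"; leukocytosis is not listed. Section 8.5, where pre-dose checks might sit, is redacted, and the Investigator's Brochure is not among the documents.

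Most of this stands, and it is why the severity is low. It does not remove the point. The general monitoring sentence names no days, the same section sends sites to the schedule for laboratory tests, and the schedule limits in-course hematology to the first day. The volunteers also did not receive glembatumumab vedotin.

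A reader might infer that the protocol leaves CDX-301 patients unmonitored, or that all eight injections are equally unguarded. The documents do not support either. Monitoring is requested in general terms, and the course 2 injections follow several counts taken after course 1.

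**Conclusion.** The point holds as a low-severity, inexpensive improvement for patient safety. In each course, four of five injections are given with no scheduled count that could show a rise caused by that course, although the plan has a withholding rule and expects the effect during administration. The finding rests on Table 2 as printed and on sites following it for laboratory timing.

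It does not establish that the threshold would be crossed. A reader might infer that patients would be dosed through dangerous leukocytosis; the visible documents give no white cell time course and no frequency, so that cannot be said. If counts peak after the fifth injection, the existing Day 1 and Day 7 samples may be well placed and in-course counts would add little. The 50,000 example is the sponsor's to set and is not in question. The practical reach is the 10 to 12 patients planned for Cohort 4, and about 30 more only if Cohort 5 opens. The SAP lists three cohorts, none receiving CDX-301.

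**What to change.** Amend the Table 2 hematology row to add a local white cell count with differential on Days -2 and 19, taken with the pre-dose CDX-301 pharmacokinetic draws that footnote 19 already schedules, and reviewed before that day's injection. This guards only the fifth injection of each course. If the sponsor wants injections 3 to 5 covered, add Days -4 and 17 as well, at the existing dosing visits. If Section 8.5 or the Investigator's Brochure already names in-course days, Table 2 should be made to match them.

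Cost of the minimum: 2 counts per patient, so 2 x 10 to 12 = 20 to 24 in Cohort 4 and 2 x 30 = 60 if Cohort 5 opens, with no new visit or needle stick. With the optional days: 4 counts per patient, so 40 to 48 and 120. Days -4 and 17 need a new draw, but the patient is already at the clinic for the injection and pre-dose vital signs. The main burden is a same-day wait for the result, which may be harder where a site uses the weekend dosing allowed in footnote 22.
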